7.2. Pharmacokinetics Assessments

7.2.1. Portion A: Single Agent PF-05082566 (Dose Escalation, and Japan Cohort(s))

Blood samples will be collected for PK of PF-05082566 at the following times:

- During Cycle 1 and Cycle 2 on (a) Day 1 at pre-dose, end of infusion, and at 1.5, 2, 6 and 24 hrs post start of infusion; (b) on Days 3, 8, 15 and 22;
- During Cycle 3 on (c) Day 1 at pre-dose, end of infusion, and at 1.5 and 24 hrs post start of infusion; (d) on Days 8, 15 and 22;
- During Cycle 4 on (e) Day 1 at pre-dose, end of infusion, and at 1.5 hr post start of infusion; (f) on Day 3 and Day 28 after administration of the last dose.

For patients ending the study, PK samples should be collected at the End of Treatment assessment day.

The PK sample for Day 28 following the Cycle 4 dose of PF-05082566 need not be collected if a patient undergoes PF-05082566 dosing for additional cycles or if the patient starts another cancer therapy. If a patient continues with additional cycles of therapy (up to 2 years), PK samples will be collected pre-dose, end of infusion and at 1.5 hours post start of infusion in each cycle.

In Japan, patients will be hospitalized for PK sampling for at least the first 2 days of the first cycle of dosing of PF-05082566 (Note: this is a planned hospitalization and thus is not considered a serious adverse event (SAE) unless prolonged due to study drugs. See section on [SAEs](#) for more information).

7.2.2. Portion B: PF-05082566 + Rituximab (Dose Escalation)

7.2.2.1. PF-05082566

Blood samples will be collected for PK of PF-05082566 at the following times:

- During Cycle 1 on (a) Day 1 at pre-dose, end of infusion, and at 1.5, 2, 6, and 24 hrs post start of infusion; (b) on Days 3, 7, 14 and 22;
- During Cycle 2 on (c) Day 1 at pre-dose, end of infusion, and at 1.5 and 24 hrs post start of infusion; (d) on Days 8, 15 and 22;
- During Cycle 3 on (e) Day 1 at pre-dose, end of infusion and at 1.5 hrs post start of infusion; (f) on Day 22;
- During Cycle 4 on (g) Day 1 at pre-dose, end of infusion and at 1.5 hrs post start of infusion; (h) and on Day 28 post Cycle 4 dose.

For patients ending from the study, PK samples should be collected at the End of Treatment assessment day.

The PK sample for Day 28 following the Cycle 4 dose of PF-05082566 need not be collected if a patient undergoes PF-05082566 dosing for additional cycles or if the patient starts another cancer therapy. If a patient continues with additional cycles of therapy up to 2 years, PK samples will be collected pre-dose, end of infusion and at 1.5 hours post start of infusion in each cycle.

7.2.2.2. Rituximab

Blood samples will be collected for PK of rituximab at the following times (NOTE: All days are numbered relative to the start of PF-05082566 dosing):

- On Day (-7) at pre-dose and at 15 min post end of infusion, 6 and 24 hrs post start of infusion;
- On Day (0) at pre-dose and 15 min post end of infusion;
- During Cycle 1 on: Day 1 at 2 and 24 hrs post start of infusion of PF-05082566; Day 3; Day 7 at pre-dose and 15 min post end of infusion; Day 14 at pre-dose and 15 min post end of infusion; and Day 22;
- During Cycle 2 on: Day 1 prior to the dose of PF-05082566 and Day 15.

For patients ending from the study, PK samples should be collected at the End of treatment assessment day.

Note that whenever rituximab PK samples are collected on days where PF-05082566 PK samples are being collected, these collections should be time matched to avoid multiple needle sticks. The time matched collections are shown in the above list in italics.

For both Portion A and Portion B, PK sampling schedule may be modified based on emerging PK data.

In addition to samples collected at the scheduled times, an additional blood sample should be collected from patients experiencing unexpected and/or serious AE's and the date and time documented in the CRF.

CCI

All efforts will be made to obtain the PK samples at the scheduled nominal time relative to dosing. However, samples obtained within 10% of the nominal time (eg, within 6 minutes of a 60 minute sample) will be considered protocol complaint, and the exact time of the sample collection noted on the CRF. If a scheduled blood sample collection cannot be completed for any reason, the missed sample time may be re-scheduled with agreement of clinical investigators, patient and Sponsor.

PK samples will be assayed for PF-05082566 and rituximab using a validated analytical method in compliance with Pfizer standard operating procedures. Details regarding the collection, processing, storage and shipping of the blood samples will be provided in the study manual.

7.2.3. Dose Expansion Cohorts – Portion A and Portion B

7.2.3.1. PF-05082566 PK Sampling for Dose Expansion Cohorts (Portions A and B)

For patients enrolled into each of the expansion cohorts for Portions A and B, blood samples will be collected for PK of PF-05082566 for at least 5 patients in each dose cohort at the following times:

- During Cycle 1 on (a) Day 1 at pre-dose, end of infusion, and at 2, 6, and 24 hrs post start of infusion; (b) one sample on Days 7 and 14, respectively;
- During Cycles 2 and 3 on (c) Day 1 at pre-dose, and end of infusion;
- During Cycle 4 on (d) Day 1 at pre-dose, and end of infusion, and 2, 6, and 24 hrs post start of infusion; (e) one sample on Days 7 and 14, respectively;
- Subsequently, every 4 cycles on Day 1 at pre-dose (Cycles 8, 12, 16, etc.);
- At the End of Treatment visit.

For the remaining patients in Portions A and B expansion cohorts, PK samples will be collected on Day 1 of Cycles 1 to 4 at pre-dose and end of infusion. After Cycle 4, PK samples will be collected on Day 1 at pre-dose every 4 cycles (Cycles 8, 12, 16, etc.). A final PK sample should be collected at the End of Treatment visit.

7.2.3.2. Rituximab PK Sampling for Dose Expansion Cohort (Portion B Only)

Blood samples will be collected for PK of rituximab for at least 5 patients enrolled in the expansion cohort for FL at the following times (NOTE: All days are numbered relative to the start of PF-05082566 dosing):

- On Day (-7) and Day (0) at pre-dose and end of infusion of rituximab;
- During Cycle 1 on: (a) Day 1 at 2 and 24 hrs post start of infusion of PF-05082566; (b) Day 7 and Day 14 at pre-dose and end of infusion of rituximab;
- During Cycle 2 on: Day 1 prior to the dose of PF-05082566;
- A final PK sample should be collected at the End of treatment visit.

For the remaining patients in Portion B expansion cohorts, PK samples for rituximab will not be collected.

Note that whenever rituximab PK samples are collected on days where PF-05082566 PK samples are being collected, these collections should be time matched to avoid multiple needle sticks.

CCI [REDACTED]

[REDACTED]

[REDACTED]

[REDACTED]

[REDACTED]

[REDACTED]

[REDACTED]

[REDACTED]

[REDACTED]

[REDACTED]

- [REDACTED]
- [REDACTED]
- [REDACTED]

[REDACTED]

CCI [Redacted]

[Redacted]

| [Redacted]

| [Redacted]

| [Redacted]

| [Redacted]

[Redacted]

[Redacted]

CCI [Redacted]

[Redacted]

CCI [Redacted]

| [Redacted]

| [Redacted]

| [Redacted]

| [Redacted]

[Redacted]

| [Redacted]

| [Redacted]

| [Redacted]

| [Redacted]

| [Redacted]

All efforts should be made to time match the PK samples with the biomarker samples whenever these samples are collected together.

CCI [REDACTED]

Flow cytometry of peripheral blood mononuclear cells (PBMCs) will also be conducted to determine the absolute counts of key cell types, including T cells B cells, and NK cells. These measurements will be used to detect changes in PBMC composition after treatment and will be conducted in parallel with the PK assessment as in [Section 7.2.1](#) and [7.2.2](#).

CCI [REDACTED]

[REDACTED]

[REDACTED]

[REDACTED]

[REDACTED]

[REDACTED]

CC [REDACTED]

[REDACTED]

[REDACTED]

[REDACTED]

[REDACTED]

[REDACTED]

[REDACTED]

[REDACTED]

[REDACTED]

7.3.3.3. Immunogenicity Assessments for Expansion Cohorts (Portion A and Portion B)

7.3.3.3.1. Immunogenicity to PF-05082566

Blood for PF-05082566 immunogenicity testing will be collected at

- Day 1 prior to the dosing of PF-05082566 for Cycles 1-4;
- After Cycle 4, ADA samples will be collected on Day 1 at pre-dose every 4 cycles (Cycles 8, 12, 16, etc.);
- End of Treatment visit.

Samples will be analyzed by a laboratory to be identified by Pfizer. See the Laboratory Manual for additional details.

7.3.3.3.2. Immunogenicity to Rituximab (Portion B Only)

Blood for rituximab immunogenicity testing (NOTE: All days are numbered relative to PF-05082566 dosing) will be collected at:

- Cycle 1 Day -7, Day 0, Day 7 and Day 14 prior to the dosing of rituximab;
- Cycle 2 Day 1 prior to the dosing of PF-05082566;
- End of treatment.

CCI [REDACTED]

[REDACTED]

[REDACTED]

[REDACTED]

[REDACTED]

[REDACTED]

[REDACTED]

[REDACTED]

CCI [Redacted]

CCI [Redacted]

CCI [Redacted]

CCI [Redacted]

[Redacted]

| [Redacted]

[Redacted]

| [Redacted]

[Redacted]

| [Redacted]

[Redacted]

[Redacted]

[Redacted]

[Redacted]

| [Redacted]

CCI [Redacted]

[Redacted]

[Redacted]

[Redacted]

[Redacted]

[Redacted]

[Redacted]

[Redacted]

[Redacted]

[Redacted] CCI

[Redacted]

CCI [Redacted]

CCI [Redacted]

[Redacted]

[Redacted]

[Redacted]

[Redacted]

[Redacted]

[Redacted]

CCI [Redacted]

[Redacted]

[Redacted]

CCI [Redacted]

[Redacted]

8. ADVERSE EVENT REPORTING

8.1. Adverse Events

All observed or volunteered AEs regardless of treatment group or suspected causal relationship to the investigational product(s) will be reported as described in the following sections.

For all AEs, the investigator must pursue and obtain information adequate both to determine the outcome of the AE and to assess whether it meets the criteria for classification as a serious adverse event (SAE) requiring immediate notification to Pfizer or its designated representative. For all AEs, sufficient information should be obtained by the investigator to determine the causality of the AE. The investigator is required to assess causality. Follow-up by the investigator may be required until the event or its sequelae resolve or stabilize at a level acceptable to the investigator, and Pfizer concurs with that assessment.

As part of ongoing safety reviews conducted by the Sponsor, any non-serious AE that is determined by the Sponsor to be serious will be reported by the Sponsor as an SAE. To assist in the determination of case seriousness further information may be requested from the investigator to provide clarity and understanding of the event in the context of the clinical study.

8.2. Reporting Period

For SAEs, the active reporting period to Pfizer or its designated representative begins from the time that the patient provides informed consent, which is obtained prior to the patient's participation in the study, ie, prior to undergoing any study-related procedure and/or receiving investigational product, through and including 60 calendar days after the last administration of the investigational product. SAEs occurring to a patient after the active reporting period has ended should be reported to the Sponsor if the investigator becomes aware of them; at a minimum, all SAEs that the investigator believes have at least a reasonable possibility of being related to investigational product are to be reported to the Sponsor.

AEs (serious and non-serious) should be recorded on the case report form (CRF) from the time the patient has taken at least one dose of investigational product through the patient's last visit.

If a patient begins a new anticancer therapy, the AE reporting period for non-serious AEs ends at the time the new treatment is started. Death must be reported if it occurs during the SAE reporting period after the last dose of investigational product, irrespective of any intervening treatment.

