5. STUDY TREATMENTS

For the purposes of this study, and per International Conference on Harmonisation (ICH) guidelines, investigational product is defined as a pharmaceutical form of an active ingredient or placebo being tested or used as a reference/comparator in a clinical trial, including a product with a marketing authorization when used or assembled (formulated or packaged) in a way different from the approved form, or when used for an unapproved indication, or when used to gain further information about an approved use (ICH E6 1.33).

For this study, the investigational products is PF-05082566. Rituximab is considered to be an investigational product in some countries and not others, according to local regulations.

Portion A:

During the dose escalation phase, PF-05082566 will be administered in escalating doses with available dose levels including the following: 0.006, 0.03, 0.06, 0.12, 0.18, 0.24, 0.30 (using the 3+3 design), and 0.6, 1.2, 2.4, 5.0 and 10 mg/kg (using the TITE-CRM design) by IV infusion of 1 hour (-5/+15 min) every 4 weeks. If a dose reduction is needed for patients being treated with 0.6 to 10 mg/kg, a dose reduction may be made from the next highest planned dose level to one of the following specific dose levels: 0.45, 0.9, 1.8, and 3.6 mg/kg. If the 10 mg/kg dose is not well tolerated, there is an option to de-escalate to 7.5 mg/kg. Each patient will initially receive the first dose on Cycle 1 Day 1 with a 28-day observation period. Cycle 2 will start on Day 29.

In the expansion cohort, PF-05082566 will be administered at either 0.24 mg/kg, 0.6 mg/kg, or 1.2 mg/kg by IV infusion of 1 hour (-5/+15 min) every 4 weeks. If a dose reduction is required due to the treatment-related toxicity, this may be allowed as an alternative to discontinuation of treatment. No dose reduction is allowed for patients treated at the 0.24 mg/kg dose level. See [Section 5.4.4](#) for details.

Japan cohort(s) in Portion A:

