Given the known side effects of rituximab and the pre-clinical and clinical safety data for PF-05082566 (see the PF-05082566 Investigator Brochure for additional details), it is not anticipated that overlapping side effects will occur. Patients will be treated with two doses of rituximab prior to the initiation of PF-05082566 to assess for rituximab specific side effects. Patients should be monitored carefully, however, for potential infusion reactions, particularly for the earlier doses of PF-05082566. Rituximab can cause severe, including fatal, infusion reactions. Severe reactions have typically occurred during the first infusion with time to onset of 30-120 minutes. Rituximab-induced infusion reactions and sequelae include urticaria, hypotension, angioedema, hypoxia, bronchospasm, pulmonary infiltrates, acute respiratory distress syndrome, myocardial infarction, ventricular fibrillation, cardiogenic shock, anaphylactoid events, or death. Refer to the rituximab package insert for additional details.

Guidance for prevention and management of infusion reactions to rituximab: Premedicate patients with an antihistamine and acetaminophen prior to dosing. For patients with rheumatoid arthritis or a previous history of rituximab-associated infusion reactions it is

suggested to administer a glucocorticoid (such as methylprednisolone) IV 30 minutes prior to each infusion. Institute medical management (eg, glucocorticoids, epinephrine, bronchodilators, or oxygen) for infusion reactions as needed. Depending on the severity of the infusion reaction and the required interventions, temporarily or permanently discontinue rituximab. Resume infusion at a minimum 50% reduction in rate after symptoms have resolved. Closely monitor the following patients: those with pre-existing cardiac or pulmonary conditions, those who experienced prior cardiopulmonary adverse reactions, and those with high numbers of circulating malignant cells. Refer to the rituximab package insert for additional details.

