8.8. Causality Assessment

The investigator's assessment of causality must be provided for all AEs (serious and non-serious); the investigator must record the causal relationship in the CRF, as appropriate, and report such an assessment in accordance with the serious adverse reporting requirements if applicable. An investigator's causality assessment is the determination of whether there exists a reasonable possibility that the investigational product caused or contributed to an AE; generally the facts (evidence) or arguments to suggest a causal relationship should be provided. If the investigator does not know whether or not the investigational product caused the event, then the event will be handled as "related to investigational product" for reporting purposes, as defined by the Sponsor (see the section on [Reporting Requirements](#)). If the investigator's causality assessment is "unknown but not related to investigational product", this should be clearly documented on study records.

In addition, if the investigator determines that an SAE is associated with study procedures, the investigator must record this causal relationship in the source documents and CRF, as appropriate, and report such an assessment in accordance with the SAE reporting requirements, if applicable.

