3.7. Baseline Variables

3.7.1. Study Drug, Study Treatment and Baseline Definitions

In this study, ‘**study drug**’ refers to PF-05082566 or rituximab and ‘**study treatment**’ (or ‘**treatment group**’) refers to one of the following:

- PF-05082566 0.006 mg/kg q4wks;
- PF-05082566 0.03 mg/kg q4wks;
- PF-05082566 0.06 mg/kg q4wks;
- PF-05082566 0.12 mg/kg q4wks;
- PF-05082566 0.18 mg/kg q4wks;
- PF-05082566 0.24 mg/kg q4wks;
- PF-05082566 0.3 mg/kg q4wks;
- PF-05082566 0.6 mg/kg q4wks;
- PF-05082566 1.2 mg/kg q4wks;
- PF-05082566 2.4 mg/kg q4wks;
- PF-05082566 5 mg/kg q4wks;
- PF-05082566 10 mg/kg q4wks;
- PF-05082566 0.03 mg/kg q4wks + rituximab 375 mg/m² q1wk x4;
- PF-05082566 0.06 mg/kg q4wks + rituximab 375 mg/m² q1wk x4;
- PF-05082566 0.12 mg/kg q4wks + rituximab 375 mg/m² q1wk x4;
- PF-05082566 0.18 mg/kg q4wks + rituximab 375 mg/m² q1wk x4;
- PF-05082566 0.24 mg/kg q4wks + rituximab 375 mg/m² q1wk x4;
- PF-05082566 0.3 mg/kg q4wks + rituximab 375 mg/m² q1wk x4;
- PF-05082566 0.6 mg/kg q4wks + rituximab 375 mg/m² q1wk x4;
- PF-05082566 1.2 mg/kg q4wks + rituximab 375 mg/m² q1wk x4;

- PF-05082566 2.4 mg/kg q4wks + rituximab 375 mg/m² q1wk x4;
- PF-05082566 5 mg/kg q4wks + rituximab 375 mg/m² q1wk x4;
- PF-05082566 10 mg/kg q4wks + rituximab 375 mg/m² q1wk x4.

Start and end dates of study treatment:

For single agent PF-05082566:

The date/time of first dose of study treatment is the earliest date/time of non-zero dosing of the study drug.

The date/time of last dose of study treatment is the latest date/time of non-zero dosing of the study drug.

For PF-05082566 + rituximab:

The date/time of first dose of study treatment in a combination arm is the earliest date/time of the first non-zero dose date/time for each of the study drugs.

The date/time of last dose of study treatment in a combination arm is the latest date/time of the last non-zero dose date/time for each of the study drugs.

Definition of baseline:

Definition of baseline for efficacy analyses in randomized cohorts

The last measurement prior to randomization will serve as the baseline measurement for efficacy analyses. If such a value is missing, the last measurement prior to the first dose of study treatment will be used as the baseline measurement except for analyses of tumor assessment data where the baseline assessment would be considered as missing.

Definition of baseline for efficacy [CCI] and for safety analyses

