5.2.7. Definition of On-treatment Period

Safety endpoints will be summarized based on the on-treatment period unless otherwise specified.

On-treatment period is defined as the time from the first dose of study treatment through minimum (30 days + last dose of study treatment, start day of new anti-cancer drug therapy – 1 day).

Safety data collected outside the on-treatment period as described above will be listed and flagged in listings but not summarized.

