6.6. Safety Summaries and Analyses

The Safety Analysis Set will be the primary population for safety evaluations. Summaries of AEs and other safety parameters will be based on the safety analysis set by treatment group.

All summaries of related AEs (PF-05082566 plus rituximab) will further be presented as PF-05082566-related, rituximab -related, or related to both study treatments.

All summaries described below by SOC and PT will further be presented by PT in decreasing frequency based on the frequencies observed in all treatment groups combined.

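### In Portion B, Section 8.2 ties the start of CRF adverse-event recording to a product status that rituximab holds only in some countries, which conflicts with the schedule, Section 7.1.2 and the SAP on-treatment period

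*Protocol*

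**What the plan says.** **When CRF recording starts.** Protocol Section 8.2 has two clocks. For reporting to the sponsor: "For SAEs, the active reporting period to Pfizer or its designated representative begins from the time that the patient provides informed consent". For the CRF, AEs of both kinds are entered "from the time the patient has taken at least one dose of investigational product".

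**What counts as investigational product.** Section 5 names PF-05082566, then adds: "Rituximab is considered to be an investigational product in some countries and not others, according to local regulations".

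**Order of dosing in Portion B.** Under Section 5, rituximab is given on Cycle 1 Day -7 and Day 0, and PF-05082566 follows on Day 1, about 24 hours after the second infusion.

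**What the SAP counts.** SAP 3.7.1 treats both drugs as study drug in every country, and the "first dose of study treatment in a combination arm is the earliest date/time of the first non-zero dose date/time" of either. SAP 5.2.7 continues: "On-treatment period is defined as the time from the first dose of study treatment". The treatment-emergent window therefore normally opens with rituximab on Day -7 for all Portion B patients.

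**Other protocol text on recording.** Table 3 leaves the AE row empty at screening and shows continuous recording from then on. Footnote 21 to Tables 3 and 4 and footnote 23 to Table 5 ask for AEs to be recorded at every visit. Footnote 7 to Tables 3 and 4 and footnote 9 to Table 5 send new or worsened conditions during trial treatment to the AE page. Section 7.1.2 sends all AEs arising during the study to that page. None of these depends on the status of rituximab.

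**Causality.** Section 8.8 asks "whether there exists a reasonable possibility that the investigational product caused or contributed to an AE". SAP 6.6 says that summaries of related AEs for the combination "will further be presented as PF-05082566-related, rituximab -related, or related to both study treatments".

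**The concern.** The protocol gives two answers to the same question: on which day does a Portion B site begin entering AEs on the CRF? Section 8.2 is the only passage that states an explicit starting trigger, and that trigger moves from Day -7 to Day 1 with the local regulatory status of rituximab. The SAP has no such dependence. A site could comply with 8.2 and still leave the first part of the SAP's treatment-emergent window empty.

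The exposed period is not a trivial one. Section 5.4 explains that the two lead-in infusions are there to reveal side effects specific to rituximab, and says of rituximab infusion reactions: "Severe reactions have typically occurred during the first infusion with time to onset of 30-120 minutes". If capture differed between countries, all-cause and rituximab-related treatment-emergent counts would be incomplete in a way that follows country mix and not treatment. The overall safety profile of the combination is a Portion B secondary objective.

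Serious events are also touched, though less. Reporting to the sponsor from consent does not depend on product status. But the CRF sentence in 8.2 covers serious events too, SAP 6.6.1 identifies SAEs from the AE eCRF page, and Protocol 8.13.2 says that the SAE form and the AE CRF are separate. A lead-in SAE could reach the safety database and be absent from the SAP tables.

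**Working it through.** **1. Length of the lead-in, checked against the SAP's own figure.** The Portion B numbering includes a Day 0.

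- Elapsed days from first rituximab to first PF-05082566: 1 - (-7) = 8.
- SAP 5.2.4 defines study day as date minus start of treatment plus 1, so the first PF-05082566 dose falls on study day 8 + 1 = 9.
- SAP 6.5.3.4 subtracts 9 when computing the Cycle 1 dose delay of PF-05082566 in Portion B. The figure is reproduced, and it confirms that the SAP starts the clock at rituximab on Day -7.

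**2. Gap under each reading.**

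| Rule followed by the site | CRF recording starts | Gap against SAP window | Rituximab infusions in the gap |
|---|---|---|---|
| 8.2 read literally, rituximab is investigational product | Day -7 | 0 days | 0 of 4 |
| 8.2 read literally, rituximab is not | Day 1 | 8 days (study days 1 to 8) | 2 of 4 |
| Table 3, AE footnotes, Section 7.1.2 | Day -7 | 0 days | 0 of 4 |

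Only the second row produces a loss.

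**3. Illustration of the exposure.** Let f be the share of patients treated where rituximab is not an investigational product and p the share with at least one AE in the lead-in. The documents give neither. If every such site read 8.2 literally, and p were the same in all countries, the number of patients per 100 with an unrecorded lead-in AE would be 100 × f × p. Section 3.1.2 plans up to 100 follicular lymphoma patients, so this is also roughly a count. With assumed values:

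| f | p = 0.20 | p = 0.40 | p = 0.60 |
|---|---|---|---|
| 0.25 | 5 | 10 | 15 |
| 0.50 | 10 | 20 | 30 |
| 0.75 | 15 | 30 | 45 |

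If sites follow the schedule, every cell is 0.

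**4. Why this is not the bias in the reported rates.** SAP 6.6.1 counts each patient once per system organ class or preferred term over the whole summary period. A patient with an unrecorded lead-in event still counts if the same term is recorded later, for example after the Day 7 or Day 14 infusion. If a fraction r of the affected patients has such a later record, the loss for that term is f × p × (1 - r), where p now refers to that term. With r anywhere from 0 to 1, the loss runs from f × p down to 0. The table in step 3 therefore bounds the lead-in loss under its assumptions; it does not estimate the error in a treatment-emergent rate.

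**The case against.** The strongest reply is that only one sentence in 8.2 is loose and the rest of the protocol is clear. Day -7 and Day 0 are scheduled Portion B visits, the footnotes require AE recording at each visit, exclusion criterion 3 says outright that study treatment includes rituximab in Portion B, and Sections 7.1.2, 8.12 and 8.13.2 place all AEs on the AE pages without condition. No document shows a site that started on Day 1. This stands, and it limits the point to a contradiction that creates a risk. A reader might infer that lead-in events are in fact captured in some countries and missed in others; the documents do not support that. What survives is that the each-visit footnotes and Section 7.1.2 state no starting trigger while 8.2 does, so a site could defend either practice.

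A second reply concerns importance. No PF-05082566 has been given in the window and rituximab is fixed at 375 mg/m², so these events cannot carry a PF-05082566 dose effect. Section 5.4.2 excludes AEs attributed to rituximab alone from the DLT definition. The SAP summarises by dose-level treatment group, not by FL-1, FL-2 and FL-3, and tests no hypothesis. Follicular lymphoma expansion patients have already received a rituximab-containing regimen of at least two doses, and intolerance to antibodies is an exclusion, so the Section 5.4 warning about first infusions may apply to them less strongly. All of this stands. It removes any real link to dose selection but leaves the all-cause and rituximab-related tables exposed.

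On causality, Sections 3.4, 5.4 and 5.4.2 already presuppose that events are attributed to rituximab, and the SAP reads a relationship field from the eCRF. Attribution is therefore expected in practice. Section 8.8 simply does not say so for a country where rituximab is outside the definition.

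**Conclusion.** The contradiction is real and worth correcting. Read literally where rituximab is not an investigational product, 8.2 leaves 8 days and 2 of 4 rituximab infusions inside the SAP on-treatment period but before CRF recording begins. The consequence would be all-cause and rituximab-related treatment-emergent counts that are incomplete and uneven by country, and possibly lead-in SAEs missing from SAP tables although reported to the sponsor.

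The size of any loss cannot be estimated from the documents. It is zero if sites followed the schedule. The 5 to 45 per 100 shown above rests on assumed f and p, equal lead-in incidence across countries and literal adherence to 8.2 at every affected site. A reader might go further and scale reported rates by (1 - f), or argue that the recommended dose is biased. Neither follows: patients are counted once per term over the whole on-treatment period, and PF-05082566-attributed rates and dose selection should be little affected by events that precede its first dose.

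One limit remains. The AE row of Table 5 is not visible in the text available for this review, so for the expansion cohorts the unconditional rule rests on footnotes 9 and 23 and Section 7.1.2.

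**What to change.** 1. **Section 8.2:** start CRF recording at the first dose of any study drug, meaning PF-05082566 or, in Portion B, rituximab, irrespective of its local regulatory status. The gap against the SAP window is then 0 days at every site.
2. **Section 8.8:** state that causality is assessed for each study drug, so that the split in SAP 6.6 has a source in every country.
3. **Patients already enrolled in Portion B:** first establish which rule each site applied. Only where recording began on Day 1, retrieve Day -7 to Day 0 events from source, or, if that is not possible, flag those patients and tabulate the lead-in separately.

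The cost is two sentences in an amendment or clarification letter and a check with Portion B sites, with data queries only where the check shows a need. No analysis method, sample size or element of patient care changes. Some reported AE counts may rise if events are recovered.
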